### **SUBJECT CHARACTERISTICS, IDENTIFICATION AND RECRUITMENT**

**Subject Selection:** Provide rationale for subject selection in terms of the scientific objectives and proposed study design.

This study will be comprised of individuals 18 years and older who participate in services provided by Safe Recovery at the Howard Center in Burlington, VT. This convenience sample was chosen based on interest from the organization to query information about current substance use behavior and potential interest in participating in an evidence-based intervention to reduce substance use.

**Vulnerable Populations:** Explain the rationale for involvement of subjects (e.g., cognitively impaired, Non-English speaking, prisoners, students). Discuss what procedures or practices will be used in the protocol to minimize their susceptibility to undue influences and unnecessary risk (physical, psychological, etc.).

**Not applicable**

Individuals who use stimulants and participate in a syringe exchange program, in order to develop more effective interventions to help them stop or reduce their stimulant use.

**Inclusion/Exclusion Criteria:** Eligibility and ineligibility criteria should be specific. Describe how eligibility will be determined and by whom. Changes to the eligibility criteria at a later phase of the research have the potential to invalidate the research.

Study participants will be individuals who participate in the syringe exchange. Participants will be recruited from the safe recovery syringe exchange program at the Howard Center – a local, community-based care center – in which they already participate.

To be included in the study, prospective participants must meet the following criteria: (a) be 18 years or older, (b) report using stimulants in the past 30 days, and (c) meet the DSM-5 diagnosis for stimulant use disorder at a moderate or severe level (i.e., 6 or more of the 11 DSM criteria), and (d) participation in services offered by Howard Center Safe Recovery

Exclusionary criteria: (a) failure to meet one or more inclusionary criteria above, (b) individuals who are cognitively impaired by their drug use or psychiatric conditions that could preclude informed consent. Specifically pertaining to criterion b: individuals who are intoxicated and/or acutely psychotic will be precluded from the study. The Howard Center staff will make this assessment based on their training and clinical judgement.

Individuals will be formally enrolled in the study if they meet all inclusionary criteria, complete the initial intake assessment, and complete the informed consent process.

**Inclusion of Minorities and Women:** Describe efforts to include minorities and women. If either minorities or women are excluded, include a justification for the exclusion.

This study will include all individuals who receive services from Safe Recovery at the Howard Center, including women and minorities.

**Inclusion of Children:** Describe efforts to include children. Inclusion is required unless a clear and compelling rationale shows that inclusion is inappropriate with respect to the health of the subjects or that inclusion is inappropriate for the purpose of the study. If children are included, the description of the plan should include a rationale for selecting or excluding a specific age range of children. When included, the plan must also describe the expertise of the investigative team in working with children, the appropriateness of the available facilities to accommodate children, and the inclusion of a sufficient number of children to contribute to a meaningful analysis relative to the purpose of the study. Provide target accrual for this population. Identify whether children are wards of the state. **If children are excluded** then provide appropriate justification.

The Safe Recovery Program primarily targets adults. Children are excluded.

For protocols including the use of an investigational drug, indicate whether women of childbearing potential have been included and, if not, include appropriate justification.

There will be no use of an investigational drug.

If HIV testing is included specifically for research purposes explain how the test results will be protected against unauthorized disclosure. Include if the subjects are to be informed of the test results. If yes, include the process and provision for counseling. If no, a rationale for not informing the subjects should be included.

Not applicable

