### **Screening**

Participants will be recruited primarily from Safe Recovery, a harm reduction facility located at the Howard

Center in Burlington, Vermont. Approximately 225 individuals per month attend Safe Recovery to exchange used syringes for new syringes. Staff at Safe Recovery estimate that approximately 25% of these individuals use cocaine and/or methamphetamine as the primary drug they inject. Individuals receiving services at Safe Recovery will be asked about interest in participation by the center research staff. Potentially eligible participants will be asked when they come in for services if they would like to participate in a research study. If interested, prospective participants will be invited to complete the intake assessment.

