### **Intervention Conditions**

Participants will be randomly assigned to one of two intervention conditions. These sessions will be administered by one of the following study team members: Howard Center research assistants, UVM research assistants helping with the project, or Drs. [name] and [name].

**Health Education Condition.** The Health Education condition is based on a previous intervention used as a control in a number of other studies (Mooney et al, 2013). Sessions consist of an educational program addressing a variety of health, wellness, and lifestyle topics adapted from a previously implemented wellness manual. One education topic will be discussed each day. The 12 daily educational topics will include: (1) stress relief, (2) nutrition, (3) hepatitis prevention, (4) HIV prevention, (5) sleep hygiene, (6) health screening, (7) meditation, (8) home emergencies, (9) healthy relationships, (10) common medical problems of people who use drugs, (11) strategies to reduce anxiety, depression and other negative moods, and (12) self-defense. Participants in this condition will be scheduled for two clinic visits per week for 12 weeks. Thus, the health education on the 12 topics listed above will be provided in addition to the services provided to all individuals in the Howard Center Safe Recovery program. At one session each week, the individual will meet with a study team member listed above who will review a topic handout with the participant. We anticipate these sessions will take approximately 10-15 minutes.

**Health Education plus Incentives for Abstinence.** Participants in the experimental condition will have the opportunity to earn financial incentives for abstaining from stimulant use, in addition to receiving the same health education as the control condition. Monitoring of stimulant use will occur through twice-weekly urinalysis during the 12 weeks of the intervention. Specimens will be screened for stimulant use using a 10-panel point-of-care test taken at the center. The financial incentives will be contingent on negative samples for stimulants which include cocaine, methamphetamine, and amphetamine. The incentive amount will start at \$25 and increase for each subsequent stimulant-negative urine sample, up to \$65 per sample. Only tests where the display indicates negative samples will result in participants earning reinforcement. The incentive amount

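### Prescribed amphetamine is not addressed at entry or in scoring, so an eligible participant taking it would count as non-abstinent for as long as it is detected

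*Combined protocol and SAP*

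**What the plan says.** **Entry.** Under Inclusion/Exclusion Criteria, a participant must "b) report using stimulants in the past 30 days, and (c) meet the DSM-5 diagnosis for stimulant use disorder", the latter at moderate or severe level. No drug is named and no positive baseline urine is required. The two exclusions are "failure to meet one or more inclusionary criteria above, (b) individuals who are cognitively impaired by their drug use or psychiatric conditions" that could prevent informed consent. Prescribed stimulants are not mentioned.

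**Test and payment.** Under Intervention Conditions, "Specimens will be screened for stimulant use using a 10-panel point-of-care test taken at the center". The ten analytes are not listed. "The financial incentives will be contingent on negative samples for stimulants which include cocaine, methamphetamine, and amphetamine". "Only tests where the display indicates negative samples will result in participants earning reinforcement". No exception and no confirmatory test is described.

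**Outcome.** Study Design, Data Collection and Statistical Considerations define the primary outcome as the percentage of point-of-care urine samples negative for stimulants, without naming drugs. Data Collection says that specimens are disposed of once the result has been recorded. Statistical Considerations and Withdrawal Procedures keep every randomised participant in the analysis.

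**Target population.** Purpose describes stimulant users in terms of cocaine and methamphetamine. Screening estimates that "approximately 25% of these individuals use cocaine and/or methamphetamine as the primary drug they inject".

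**The concern.** The outcome is meant to measure abstinence from the stimulant use that brought the person into the trial. Amphetamine is expressly on the list of counted drugs, and a person can take it on prescription. Someone with cocaine use disorder and such a prescription meets every entry criterion. That person could stop cocaine completely and still give a positive sample at each visit.

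Two things follow. The primary outcome does not respond to that person's behaviour. In the incentive arm, the payment cannot reach them either, because it depends on the same display. Intent-to-treat rightly keeps them in the analysis, and the plan gives no rule for scoring them differently. With about 20 per arm, even one or two such people matter to an estimate that is meant to inform a larger trial.

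**Working it through.** **Step 1: follow one participant through the rules.** Take a cocaine user with at least 6 DSM-5 criteria, use in the past 30 days and a current amphetamine prescription.

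- Eligible: yes, since no criterion refers to the prescription.
- Sample result: positive for amphetamine while the medicine is taken and detected. The outcome definition lists no drugs, so I carry over the list from the incentive rule.
- Payment in the incentive arm: none on those samples. The plan's maximum reproduces: 17 samples rising from $25 to $65 in steps of $2.50 give 17 × 45 = $765, seven more at $65 give $455, and the total is $1,220. This participant could earn none of it while the medicine is detected.
- Later correction: not possible. The specimen is gone, and the plan does not say that results are kept by drug.

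**Step 2: size of the effect on the estimate.** The plan gives no figure on this point. From the documents: 40 participants. Assumed: 1:1 allocation (20 per arm; the ratio is not stated), true abstinence of 20% in control and 45% with incentives (illustrative), and affected participants positive throughout the 12 weeks (the worst case). With k affected participants in an arm, the observed rate is (1 − k/20) × true rate.

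| Affected: incentive / control | Incentive rate | Control rate | Difference |
|---|---|---|---|
| 0 / 0 | 45% | 20% | 25 points |
| 1 / 1 | 0.95 × 45 = 42.75% | 0.95 × 20 = 19% | 23.75 |
| 2 / 2 | 0.90 × 45 = 40.5% | 0.90 × 20 = 18% | 22.5 |
| 1 / 0 | 42.75% | 20% | 22.75 |
| 0 / 1 | 45% | 19% | 26 |

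With equal numbers in the arms, the difference is multiplied by (1 − k/20) whatever the true rates: a 5% loss for one per arm and 10% for two. With unequal numbers, it moves either way.

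**Step 3: power.** Take the plan's d = 0.51 and 20 per arm, and let the effect shrink to 0.51 × (1 − f) for an affected share f, with the standard deviation held constant. Power is approximately Φ(d√(20/2) − 1.96).

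- f = 0: Φ(1.613 − 1.96), about 36%
- f = 5% (2 of 40): Φ(1.532 − 1.96), about 33%
- f = 10% (4 of 40): Φ(1.452 − 1.96), about 31%

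Power is already low in this pilot, and the further loss is small.

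**The case against.** The strongest reply is that the documents read together make the intended meaning clear. Purpose glosses stimulants as cocaine and methamphetamine, and Screening expects people who mainly inject those drugs. Nothing shows that anyone with an amphetamine prescription attends the site. The intake survey's items are not reproduced and the procedures checklist ticks medical history, so prescriptions may already be asked about. The trial is described as an exploratory pilot, not one powered for efficacy.

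Much of this stands. The number affected may be zero, and I cannot say that prescriptions go unrecorded. But the intended meaning does not close the gap: a cocaine user with a prescription is squarely in the target population, and amphetamine is explicitly counted. Even if prescriptions are recorded at intake, no stated rule uses them for eligibility or scoring.

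Excluding prescription holders would also remove the problem. It is a trade-off rather than a necessary correction, because it would narrow a trial in a low-barrier service whose aims include feasibility and acceptability.

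**Conclusion.** The gap is real and its expected size is modest. As written, the rules score an eligible participant as non-abstinent because of a prescribed medicine, and the data needed to repair this are not kept. One affected participant in each arm of 20 costs 5% of the effect, and a single affected participant in one arm moves an assumed 25-point difference to 22.75 or 26. These figures rest on 1:1 allocation, illustrative rates, and the medicine being detected throughout. The frequency is unknown.

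Three stronger readings are tempting but not supported:

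- *That users of other stimulants could never test positive and would be paid the maximum.* The incentive rule lists drugs that stimulants include, the ten analytes are not given, and any use of cocaine, methamphetamine or amphetamine would still show. The documents give no sign of a participant whose only stimulant is off the panel.
- *That two people could remove a quarter of the effect.* This needs such an always-negative person in control (0.95 × 20 + 5 = 24%) together with an always-positive person in the incentive arm (42.75%), leaving 18.75 points. The reverse pairing gives 47.75 − 19 = 28.75, so the first figure is only the worst case.
- *That the comparison is systematically biased.* Randomisation spreads prescription holders evenly on average. What remains is dilution and chance imbalance.

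**What to change.** 1. In Inclusion/Exclusion Criteria, name cocaine, methamphetamine or non-prescribed amphetamine in criterion (b), and require in (c) that the disorder concern at least one of them.
2. Record current amphetamine-class prescriptions at intake, before randomisation.
3. Record the cocaine, methamphetamine and amphetamine strips as separate fields at each visit, and list the panel's analytes. Confirm from the test's product information that the three are read separately and that the prescribed medicine does not also turn the methamphetamine strip positive; the analysis in item 4 assumes both.
4. Prespecify an analysis of the primary outcome in which participants with a documented prescription are scored on the cocaine and methamphetamine strips only, and everyone else on all three. Dropping the amphetamine strip for everyone would score an amphetamine-only user as abstinent.

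**Cost.** A few data fields and one extra analysis. Non-prescribed amphetamine use by prescription holders would be missed in that analysis. Recruitment should hardly suffer: the plan's own figures give 225 × 0.25 ≈ 56 people a month who mainly inject cocaine or methamphetamine, for 40 places.

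**Limit.** The analysis repairs scoring, not payment. Under the display-only rule a prescription holder in the incentive arm stays unpaid. If that person behaves as a control would, the arm's rate is 0.95 × 45 + 0.05 × 20 = 43.75%, and the difference is again 23.75 points. A holder in the control arm no longer shifts the estimate. The protocol should say how the payment rule treats such participants; that choice is for the sponsor.

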**Will the SONA Psychology Pool be utilized? Include documentation indicating permission to use this recruiting tool**

Yes  No

### **FINANCIAL CONSIDERATIONS**

**Describe all potential research related expenses to subjects:**

There are no expenses for participants.

**Compensation for participation:** Describe all plans to pay subjects, either in cash, a gift or gift certificate. Please note that all payments must be prorated throughout the life of the study. The IRB will not approve a study where there is only a lump sum payment at the end of the study because this can be considered coercive. The amount of payment must be justified. Clarify if subjects will be reimbursed for travel or other expenses.

**Not applicable**

All prospective participants will complete a formal assessment at intake for which they will receive \$25 for completing the assessment. All participants will complete the questionnaires for decision making task and demand for substances three additional times after baseline, at weeks 4, 8, and 12, and will be compensated \$10 per assessment independent of substance use status to ensure high compliance. If randomized to Intervention A, participants can earn \$10 for providing each urine sample twice per week (total up to \$240); the incentive is not contingent on a stimulant negative urine sample (i.e., is only contingent on providing the sample). Thus, the maximum amount a participant can earn in Intervention A is \$295. If randomized to Intervention B, urine samples will be collected for participants twice weekly for 12 weeks where participants can earn incentives by providing a negative urine sample (i.e., the incentive is contingent on providing a stimulant negative urine sample). Incentives for these samples start at \$25 and max out at \$65 (max total - \$1,220). Thus, the maximum amount a participant can earn is \$1,275. All compensation will be delivered on a gift card or a reloadable debit card.

**Research Data Management Plan:** The Research Data Management and Security Plan form must be completed. The form, along with guidance, can be found in our [forms library](#) and must be submitted with your initial application.
